1.3. Schedule of Activities (SoA)

Phase	Screeninga	Baseline		48-Weeks Treatment Phase ^c					ESIDe	30-Day FU ^f	Remarks
Visit		Day 1 ^b	Week 4	Week 12	Week 24	Week 28 ^d	Week 36	Week 48			
Study Procedures										_	
Screening/Administrative											
Informed consent	X										Must be obtained before the first study related activity.
Medical history	X										
Height	Х										Measured using a wall mounted stadiometer or one mounted on a balance beam scale, whichever is most appropriate for the individual participant. Participants should be wearing socks or barefoot and should not be wearing shoes.
HBV and HCV testing	X										
Serum pregnancy test	X										Females of childbearing potential only; at central laboratory
FSH test	X										FSH test for female participants who have stopped menstruating for at least 2 years but do not have documentation of ovarian failure.
Inclusion/exclusion criteria	X	Х									If a participant's clinical status changes (including any available laboratory results or receipt of additional medical records) after screening but before the first dose of D/C/F/TAF FDC is given such that he/she no longer meets all eligibility criteria, then the participant should be excluded.
Study Intervention											
Randomization		X									Randomization should be performed on the same day as the baseline visit, provided that all screening procedures have been completed and participant eligibility has been confirmed.
D/C/F/TAF Dispensation/Accountability		X	X	X	X		X	X	X		Immediate Switch Arm
D/C/F/TAF Dispensation/Accountability					X	X	X	X	X		Delayed Switch Arm

Phase	Screening ^a	Baseline		48-W	eeks Trea	atment P	hase ^c		ESIDe	30-Day FU ^f	Remarks
Visit		Day 1 ^b	Week 4	Week 12	Week 24	Week 28 ^d	Week 36	Week 48			
Study Procedures											
Adherence		Х	X	X	X	X	X	X	X		Treatment adherence will be assessed by participant self report using a 4 day recall during study visit.
Safety Evaluations											
Vital signs	X	X	X	X	X	X	X	X	X	X	BP, pulse rate (supine after at least 5 minutes rest)

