- d For participants randomized to the Delayed Switch arm; 4 weeks after switch to D/C/F/TAF FDC.
- e Participants who prematurely discontinue or change study intervention during the treatment phase (from Day 1 to Week 48) will be required to complete the early study intervention discontinuation (ESID) visit assessments within 1 week of stopping/changing study intervention.
- f Required for any participant who has an ongoing adverse event (AE) or serious adverse event (SAE) at the time of his/her last study visit (unless consent is withdrawn); ±7 days window may be used.

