To assess viral resistance in participants with confirmed HIV-1 RNA rebound for participants switching to D/C/F/TAF FDC (Immediate Switch Arm) compared to continuing the current INI + TAF/FTC ARV regimen (Delayed Switch Arm) DROPE	 Proportion of participants with pre-baseline PR, RT, and INI RAMs based on historical genotypes Incidence of observed genotypic and phenotypic ARV resistance for participants meeting HIV-1 RNA rebound criteria through Week 24 Proportion of participants with newly identified post-baseline RAMs and phenotypic resistance compared to pre-baseline resistance tests when available, upon meeting confirmed virologic rebound through Week 24
PROs	
To assess changes in the burden of common symptoms associated with HIV treatment or disease for participants switching to D/C/F/TAF FDC (Immediate Switch Arm) compared to continuing the current INI + TAF/FTC ARV regimen (Delayed Switch Arm)	 Change from Baseline in the proportion of participants who have bothersome symptoms (scores of 2, 3 or 4) across all items of the HIV-SI at Week 24 Change from Baseline in the proportion of participants who have any symptoms (scores of 1, 2, 3 or 4) across all items of the HIV-SI at Week 24 Association between treatment arm and each bothersome symptom of the HIV-SI adjusting for Baseline variables at Week 24

Objectives	Endpoints
To describe responses on the PGIC in participants switching to D/C/F/TAF FDC (Immediate Switch Arm) and in participants continuing the current INI + TAF/FTC ARV regimen (Delayed Switch Arm)	PGIC at Week 24
Adherence	
To evaluate adherence in participants switching to D/C/F/TAF FDC (Immediate Switch Arm) compared to continuing the current INI + TAF/FTC ARV regimen (Delayed Switch Arm)	Adherence rates by participant self-report using 4-day recall at Weeks 4, 12 and 24
Exploratory	
Exploratory clinical biomarker	
To assess changes in alpha-melanocyte stimulating hormone when switching to D/C/F/TAF FDC (Immediate Switch Arm) compared to continuing the current INI + TAF/FTC ARV regimen (Delayed Switch Arm)	Change from Baseline in alpha melanocyte-stimulating hormone at Week 24
Exploratory PROs	
To assess changes in eating-related concepts (hunger, appetite, cravings, and satiety) for participants switching to D/C/F/TAF FDC (Immediate Switch Arm) compared to continuing the current INI + TAF/FTC ARV regimen (Delayed Switch Arm)	Change from Baseline in the scores on the DAILY EATS at Week 24

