To evaluate adherence in participants switching to D/C/F/TAF FDC (Immediate Switch Arm)	 Adherence rates by participant self-report using 4-day recall at Weeks 36 and 48
Exploratory	
Exploratory clinical biomarker	
To assess changes in alpha melanocyte-stimulating hormone when switching to D/C/F/TAF FDC (Immediate Switch Arm)	Change from Baseline in alpha melanocyte-stimulating hormone at Week 48
Exploratory PROs	
To assess changes in eating-related concepts (hunger, appetite, cravings, and satiety) for participants switching to D/C/F/TAF FDC (Immediate Switch Arm)	Change from Baseline in the scores on the DAILY EATS at Week 48
To assess changes in concerns about body shape for participants switching to	• Change from Baseline in the scores on the BSQ-8D at Week 48

CONFIDENTIAL – FOIA Exemptions Apply in U.S.

Objectives	Endpoints
D/C/F/TAF FDC (Immediate Switch Arm)	• Change from Baseline in the proportion of participants who have no concern (<19), mild concern (19-25), moderate concern (26-33) or marked concern (>33) with their body shape on the BSQ-8D at Week 48

Abbreviations: AE: adverse event, ARV: antiretroviral, BMI: body mass index, BSQ 8D: body shape questionnaire, D/C/F/TAF FDC: Darunavir/Cobicistat/Emtricitabine/Tenofovir Alafenamide Fixed dose Combination, DBP: diastolic blood pressure, DEXA: dual energy X ray absorptiometry, FDA: Food Drug Administration, FTC: emtricitabine, HAIR: hypertension, age, insulin, resistance, HIV 1 RNA: human immunodeficiency virus type 1 ribonucleic acid, HIV SI: HIV Symptom Index, HOMA IR: homeostatic model assessment of insulin resistance, INI: integrase, NAFLD: non alcoholic fatty liver disease, NASH: Nonalcoholic fatty liver disease, PGIC: patient global impression of change, PR: protease, PROs: patient reported outcomes, RT: reverse transcriptase, SAE: serious adverse event, SBP: systolic blood pressure.

3.3. Consistency of Effect of Baseline to Week 24 (Immediate Switch) versus Week 24 to Week 48 (Delayed Switch)

Additional secondary objectives/endpoints will evaluate the consistency of effect on outcomes from Baseline to Week 24 in the Immediate Switch Arm versus the Week 24 to Week 48 in the Delayed Switch Arm. The endpoints for the Delayed Switch Arm from Week 24 to Week 48 are the same as for the Immediate Switch to Week 24. Comparison will be made descriptively to evaluate the consistence of outcomes between these two arms for each endpoint.

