- Incidence of observed genotypic and phenotypic resistance for participants meeting HIV-1 RNA rebound criteria at Week 24 (Immediate Switch Arm) compared to the incidence of observed genotypic and phenotypic resistance for participants meeting HIV-1 RNA rebound criteria from Week 24 to Week 48 (Delayed Switch Arm)
- Proportion of participants with baseline DRV, FTC, TFV and INI RAMs based on historical genotypes
- Proportion of participant with identified post-baseline RAMs and loss of phenotypic susceptibility, when available, upon meeting confirmed virologic rebound at Week 24 (Immediate Switch Arm) compared to proportion of participant with identified post-baseline RAMs and loss of phenotypic susceptibility, when available, upon meeting confirmed virologic rebound from Week 24 to Week 48 (Delayed Switch Arm)

PROs:

- Change in the proportion of participants who have bothersome symptoms (scores of 2, 3 or 4) across all items of the HIV-SI from Baseline to Week 24 (Immediate Switch Arm) compared to the Change in the proportion of participants who have bothersome symptoms (scores of 2, 3 or 4) across all items of the HIV-SI from Week 24 to Week 48 (Delayed Switch Arm)
- Change in the proportion of participants who have any symptoms (scores of 1, 2, 3 or 4) across all items of the HIV-SI from Baseline to Week 24 (Immediate Switch Arm) compared to the change in the proportion of participants who have any symptoms (scores of 1, 2, 3 or 4) across all items of the HIV-SI from Week 24 to Week 48 (Delayed Switch Arm)
- PGIC and PGIC-S at Week 24 (Immediate Switch Arm) and PGIC and PGIC-S at Week 48 (Delayed Switch Arm)

Adherence:

• Adherence rates by participant self-report using 4-day recall at Weeks 12 and 24 (Immediate

Switch Arm) compared to the Adherence rates by participant self- report using 4-day recall at Weeks 36 and 48 (Delayed Switch Arm).

Exploratory:

Exploratory clinical biomarker:

• Change in alpha stimulating-melanocyte hormone from Baseline to Week 24 (Immediate Switch Arm) compared to the change in alpha stimulating melanocyte hormone from Week 24 to Week 48 (Delayed Switch Arm).

Exploratory PROs:

- Change in the scores on the DAILY EATS from Baseline to Week 24 (Immediate Switch Arm) compared to the change in the scores on the DAILY EATS from Week 24 to Week 48 (Delayed Switch Arm)

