6.2.2.3. Adherence Analyses

Adherence rates will be reported according to the proportion of participants missing 0, 1, 2, 3 or 4 doses using participant self-report 4-day recall at Weeks 4, 12, 24, 36, and 48.

Treatment adherence based on participant self-report using a 4-day recall will be summarized descriptively and frequency tabulations for both D/C/F/TAF FDC and the INI + TAF/FTC ARV regimen. Cumulative treatment adherence through Week 48 will be determined. Additionally, all self-reported adherence will be listed.

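### The SAP's adherence consistency comparison leaves out the 4-week post-switch pair (Week 4 against Week 28) that Protocol 3.3, read with 3.1, calls for, and no adherence summary that names its visits includes Week 28

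*SAP*

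**What the plan says.** Protocol 3.3 sets the rule for the consistency comparison: "The endpoints for the Delayed Switch Arm from Week 24 to Week 48 are the same as for the Immediate Switch to Week 24". It adds: "Comparison will be made descriptively to evaluate the consistence of outcomes between these two arms for each endpoint".

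Protocol 3.1 defines the adherence endpoint over the first 24 weeks: "Adherence rates by participant self-report using 4-day recall at Weeks 4, 12 and 24".

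SAP 6.2.1.1, under Adherence, takes "Adherence rates by participant self-report using 4-day recall at Weeks 12 and 24" for the Immediate arm and sets it against the Delayed arm's "report using 4-day recall at Weeks 36 and 48 (Delayed Switch Arm".

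The Schedule of Activities (Protocol 1.3) marks adherence at Day 1, at Weeks 4, 12, 24, 28, 36 and 48, and at the early discontinuation visit, with the remark "Treatment adherence will be assessed by participant self report using a 4 day recall during study visit". Its footnote to the Week 28 column reads "For participants randomized to the Delayed Switch arm; 4 weeks after switch to D/C/F/TAF FDC". SAP 4.3 likewise has adherence assessed at every study visit.

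The by-visit tabulation in SAP 6.2.2.3 uses "4-day recall at Weeks 4, 12, 24, 36, and 48". SAP 4.3 and 6.2.1, Protocol 9.4.3.3 and the Protocol synopsis give the same five weeks. SAP 6.2.2.3 also plans descriptive summaries and frequency tables by regimen without naming visits, a cumulative adherence measure through Week 48, and a listing of all self-reports.

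**The concern.** The consistency comparison asks whether switching to D/C/F/TAF gives similar results in the two arms, so each arm should be read at the same times after its own switch. The Protocol fixes those times through 3.1 and 3.3, and the SAP uses fewer of them. The pair left out is the earliest: the only scheduled post-switch visit before 12 weeks in either arm.

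At stake is whether the comparison says anything about adherence soon after the change of regimen. Protocol 2.3.2 accepts that a switch can always bring new adverse drug reactions, so an early reading is of some interest in a tolerability study. As the SAP stands, the Delayed arm's first on-D/C/F/TAF self-report is collected but appears by name in no planned by-visit summary.

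**Working it through.** No sample size, power or error rate is involved. The check is a comparison of visit sets on the scale of weeks since starting D/C/F/TAF.

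**Time scale.** For the Immediate arm, weeks since the switch = study week. For the Delayed arm, weeks since the switch = study week − 24, taking the switch to occur at the Week 24 visit as both documents plan.

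**What the Protocol implies.**
- Immediate arm (Protocol 3.1): study Weeks 4, 12 and 24, so {4, 12, 24}.
- Delayed arm (scheduled visits after Week 24): 28 − 24 = 4, 36 − 24 = 12, 48 − 24 = 24, so {4, 12, 24}.
- The sets coincide, giving three matched pairs.

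**What SAP 6.2.1.1 does.**
- Immediate arm: {12, 24}.
- Delayed arm: 36 − 24 = 12, 48 − 24 = 24, so {12, 24}.

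| Weeks since switch | Immediate arm | Delayed arm | Implied by Protocol 3.1 and 3.3 | In SAP 6.2.1.1 |
|---|---|---|---|---|
| 4 | Week 4 | Week 28 | Yes | No |
| 12 | Week 12 | Week 36 | Yes | Yes |
| 24 | Week 24 | Week 48 | Yes | Yes |

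**Are the missing data available?** Yes. The Schedule of Activities marks adherence at both Week 4 and Week 28. SAP 2.2 gives Week 28 its own window in the Delayed arm (Days 183 to 224, target Day 197). Week 36 in that arm runs from Day 225 to Day 294. The windows do not overlap, and a visit assigned to one window is not reused for a later time point. A Week 28 report therefore cannot reach the comparison through the Week 36 column.

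**Does another named analysis cover it?** Each adherence summary that lists its visits was read:
- Protocol synopsis and 9.4.3.3: Weeks 4, 12, 24, 36, 48.
- SAP 4.3, 6.2.1 and 6.2.2.3: Weeks 4, 12, 24, 36, 48.

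None includes Week 28. Protocol 3.2 names Weeks 36 and 48 for adherence, but for the Immediate arm, which has no Week 28 visit, so it does not explain the omission in the Delayed arm.

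**Is the omission explained?** The SAP's amendment history does not mention it, and SAP 6.2.1.1 gives no reason.

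**The case against.** The strongest case on the other side is that little is lost. SAP 6.2.2.3 goes beyond its five named visits: its by-regimen tabulations carry no visit restriction, its cumulative measure runs through Week 48, and every self-report is to be listed. A reader might infer that the Week 28 data are used nowhere. The documents do not support that: the values will appear in the listing and may enter the other two outputs, whose derivation is not given. This part of the objection stands, and it limits the second half of the point to summaries that name their visits.

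It can also be said that the SAP only follows the Protocol. For the by-visit list this is right: Protocol 9.4.3.3 and the synopsis have the same five weeks, so the Protocol is out of step with its own 3.3 and Schedule of Activities. It does not cover SAP 6.2.1.1, where Week 4 is dropped as well as Week 28, against Protocol 3.1 and 3.3.

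A reader might go further and infer that leaving out the early pair makes adherence look better, or the arms more alike, than they are. Neither document says that missed doses concentrate in the first weeks after a switch. Each report covers four days only, the omission applies to both arms, and the Immediate arm's Week 4 result is still tabulated elsewhere. No direction can be claimed.

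Nor do the documents say that adherence is collected at Week 28 for the sake of this comparison. It is marked at every scheduled visit from Day 1, so Week 28 may be routine collection.

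**Conclusion.** The point holds in limited form. SAP 6.2.1.1 departs from Protocol 3.3 read with 3.1 by omitting the Week 4 against Week 28 adherence pair, and no adherence summary in either document that names its visits includes Week 28.

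The size is one of three matched pairs in one descriptive secondary comparison. It would be tempting to call this a loss of a third of the Delayed arm's on-treatment adherence data. That counts scheduled visits rather than data, leaves out early discontinuation visits, and treats as lost what is collected and will be listed. The hypothesis test, the significance level, the sample size and the primary analysis are not affected.

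The conclusion rests on two assumptions: that the same endpoints in Protocol 3.3 means the same times since the switch, which the Week 28 footnote supports, and that the Delayed arm switches at the Week 24 visit.

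**What to change.** - In SAP 6.2.1.1, compare adherence at Weeks 4, 12 and 24 (Immediate arm) with Weeks 28, 36 and 48 (Delayed arm).
- Add Week 28, Delayed arm only, to the by-visit adherence lists in SAP 4.3, 6.2.1 and 6.2.2.3.
- Make the same addition in Protocol 9.4.3.3 and the synopsis, so that the SAP does not then differ from the Protocol.
- State in SAP 6.2.2.3 how cumulative adherence is derived and whether it and the by-regimen tables include Week 28.

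The cost is a few lines of wording and one more column in the adherence tables. Collection, visit windows and the primary analysis do not change.

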6.2.2. Secondary Analysis Methods

6.2.2.1. Metabolic Analyses

Secondary metabolic endpoints will be analyzed using descriptive statistics and frequency tabulations.

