Plasma samples may be used to evaluate the concentration of DRV and COBI in participants experiencing confirmed virologic rebound using stored blood samples collected throughout the study at the discretion of the sponsor. Plasma concentrations of INIs for the Delayed Switch arm may be determined in participants experiencing confirmed virologic rebound using stored blood samples collected throughout the study, if deemed necessary by the sponsor.

STATISTICAL METHODS

Statistical Hypothesis

The statistical hypothesis is the following:

 H_0 : Dt -Dc=0 vs. H_1 : Dt -Dc $\neq 0$.

Where H₀ is the null hypothesis, H₁ is the alternative hypothesis; Dt=%body weight change from baseline at Week 24 for treatment D/C/F/TAF, Dc for the Delayed Switch arm.

The statistical hypothesis will be tested using repeated measures longitudinal method (linear mixed-effects model) at 0.05 significance level, 2-sided.

For all participants who receive at least 1 dose of study intervention descriptive statistics will be provided. Participant information will be analyzed based on the Intent-to-treat (ITT) population, unless otherwise specified.

Primary Endpoint Analysis: The primary endpoint analysis will be based on the ITT population. It will be evaluated using linear mixed-effects model with participant as random effect adjusted by baseline BMI and stratification factors in a longitudinal data with repeated measures (percent body weight change measured at multiple visits).

Secondary Endpoint Analyses:

Metabolic Analyses: For the metabolic endpoints of change from baseline, the same statistical model as described for the primary endpoint will be used for analysis. Other secondary metabolic endpoints will be analyzed using descriptive statistics.

Resistance/Efficacy Analyses: HIV-1 genotypes, and phenotypes if applicable, will be analyzed from samples of participants with virologic rebound and with HIV-1 RNA ≥400 copies/mL.

Virologic suppression (HIV-1 RNA<50 copies/mL) and failure (HIV-1 RNA ≥50 copies/mL) using the Food and Drug Administration (FDA) Snapshot algorithm in the ITT will also be analyzed as a secondary endpoint at Weeks 24 and 48.

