9.4.3. Secondary Analyses

9.4.3.1. Metabolic Analyses

For the metabolic endpoints of change from baseline, the same statistical model as described for the primary endpoint will be used for analysis. All other endpoints will be analyzed using descriptive statistics.

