1.1.2. Secondary Objectives

1.1.2.1. Week 24 Objectives

Metabolic:

- To assess changes in body weight when switching to D/C/F/TAF FDC (Immediate Switch Arm) compared to continuing the current INI + TAF/FTC ARV regimen (Delayed Switch Arm)
- To assess changes in body composition when switching to D/C/F/TAF FDC (Immediate Switch Arm) compared to continuing the current INI + TAF/FTC ARV regimen (Delayed Switch Arm)
- To assess change in blood pressure when switching to D/C/F/TAF FDC (Immediate Switch Arm) compared to continuing the current INI + TAF/FTC ARV regimen (Delayed Switch Arm)
- To assess changes in clinical laboratory tests when switching to D/C/F/TAF FDC (Immediate Switch Arm) compared to continuing the current INI + TAF/FTC ARV regimen (Delayed Switch Arm)
- To assess changes in liver biomarkers when switching to D/C/F/TAF FDC (Immediate Switch Arm) compared to continuing the current INI + TAF/FTC ARV regimen (Delayed Switch Arm)
- To assess changes in concomitant medications of interest (including anti- hypertensive, anti-hyperglycemic, and lipid lowering agents) when switching to D/C/F/TAF FDC (Immediate Switch Arm) compared to continuing the current INI + TAF/FTC ARV regimen (Delayed Switch Arm)

Safety:

• To evaluate the safety of switching to D/C/F/TAF FDC (Immediate Switch Arm) compared to continuing the current INI + TAF/FTC ARV regimen (Delayed Switch Arm)

Efficacy:

- To evaluate the virologic outcomes when switching to D/C/F/TAF FDC (Immediate Switch Arm) compared to continuing the current INI + TAF/FTC ARV regimen (Delayed Switch Arm)
- To evaluate immunological changes when switching to D/C/F/TAF FDC (Immediate Switch Arm) compared to continuing the current INI + TAF/FTC ARV regimen (Delayed Switch Arm)

Resistance:

• To assess viral resistance in participants with confirmed HIV-1 RNA rebound for participants switching to D/C/F/TAF FDC (Immediate Switch Arm) compared to continuing the current INI + TAF/FTC ARV regimen (Delayed Switch Arm)

PROs:

- To assess changes in the burden of common symptoms associated with HIV treatment or disease for participants switching to D/C/F/TAF FDC (Immediate Switch Arm) compared to continuing the current INI + TAF/FTC ARV regimen (Delayed Switch Arm)
- To describe responses on the PGIC in participants switching to D/C/F/TAF FDC (Immediate Switch Arm) and in participants continuing the current INI + TAF/FTC ARV regimen (Delayed Switch Arm)

Adherence:

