5. METABOLIC/WEIGHT

5.1. Analysis Specification

In general, continuous variables will be summarized using descriptive statistics including the number of participants, mean, standard deviation (SD), two-sided 95% confidence interval (CI), median, and range. Binary or categorical variables will be summarized using the number and percentage of participants in each category. Descriptive summaries will be provided by stratification factors (sex and race). Graphic displays will also be used to summarize the data.

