6.2. Secondary Endpoints and Analysis Methods

6.2.1. Weeks 24 and 48 Endpoints

In the following, the secondary endpoints at Week 24 are defined for D/C/F/TAF FDC regimen (Immediate Switch Arm) versus INI + TAF/FTC ARV regimen (Delayed Switch Arm), while the secondary endpoints at Week 48 are related to D/C/F/TAF FDC (Immediate Switch Arm) only.

Metabolic:

- Change from Baseline in absolute body weight over time
- Proportion of participants with % change from baseline in body weight >5% over time.
- Proportion of participants with % change from baseline in body weight >3% over time.
- Change from Baseline in BMI over time.
- Change from Baseline in body composition as measured by DEXA scan at Week 24 and Week 48, respectively.
- Change from Baseline in waist circumference over time.
- Change in SBP and DBP from Baseline over time.
- Change from Baseline in fasting lipids over time.
- Change from Baseline in fasting glucose over time.
- Change from Baseline in HOMA-IR at Week 24 and Week 48, respectively.
- Change from Baseline in HbA1c at Week 24 and Week 48, respectively.
- Change from Baseline in leptin and adiponectin at Week 24 and Week 48, respectively.
- Change from Baseline in the proportion of participants with advanced fibrosis according to the NAFLD fibrosis score at Week 24 and Week 48, respectively.
- Change from Baseline in the proportion of participants at high risk of NASH according to the HAIR score at Week 24 and Week 48, respectively.
- Proportion of participants having a dose-reduction or complete withdrawal of anti-hypertensive, anti- hyperglycemic, or lipid lowering agents in the Immediate Switch Arm from Baseline to Week 24 and Week 48, respectively or Delayed Switch Arm from Baseline to Week 24.
- Proportion of participants initiating an anti-hypertensive, anti-hyperglycemic, or lipid lowering agent in the Immediate Switch Arm from Baseline to Week 24 and Week 48, respectively or Delayed Switch Arm from Baseline to Week 24.

Safety:

- Incidence of any Grade AEs (related and not related) through Week 24 and Week 48, respectively.
- Incidence of Grade 3 and 4 AEs (related and not related) through Week 24 and Week 48,

- respectively.
- Incidence of discontinuations due to AEs through Week 24 and Week 48, respectively.
- Incidence of SAEs (related and not related) through Week 24 and Week 48, respectively.
- Change from Baseline in clinical laboratory tests over time.
- Incidence of Grade 3 and 4 laboratory abnormalities over time.

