7.2.2. Analysis Methods

Descriptive statistics will be presented for all chemistry, hematology, and urinalysis laboratory tests at scheduled time points. If there are retesting, repeating the same analyze from same collected sample, last or retested results will be used in analysis.

Change from baseline to each scheduled time points will be summarized descriptively for chemistry, hematology, and urinalysis (pH, and specific gravity) tests. A box plot of change from baseline to analysis timepoints will be provided for the following laboratory tests: eGFR, ALT and AST.

Cross-tabulations for the worst toxicity grades through Weeks 24 and 48, respectively, versus reference per laboratory test, and cross-tabulations of the worst toxicity grades at Weeks 24 and 48, respectively, versus reference will also be provided if applicable. Subject listings of abnormal laboratory values will be provided.

Descriptive statistics by Division of AIDS (DAIDS) toxicity grade over time will be presented. Shift summaries from baseline DAIDS toxicity grade to the worst on-treatment toxicity grade will also be presented.

If the DAIDS grading is not available, shift tables will be provided summarizing the shift in laboratory values from baseline to weeks 24 and 48 analysis time points with respect to abnormality criteria (low, normal, high).

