7.3.2. Analysis Methods

Continuous vital sign parameters including height, weight, pulse, blood pressure (systolic and diastolic), and Body Mass Index (BMI) will be summarized at each assessment time point by descriptive statistics (mean, standard deviation, median, minimum and maximum) per treatment arm.

Cross-tabulations for the worst abnormalities versus reference per vital signs test will be produced by treatment arm.

Descriptive statistics for the actual values and changes from baseline (including BMI, weight) per timepoint will be presented. The only reference time point that will be used to calculate these changes is the timepoint closest to the first drug intake after randomization.

BMI will be calculated as weight (kg)/(height (m²)), at each time point that body weight is measured. The height measurement collected at screening will be used in the calculation. The frequency tabulations will be presented for BMI as a categorical variable and the descriptive statistics will be summarized for BMI as a continuous variable.

Physical examination findings and changes from baseline at each scheduled time point will be tabulated per treatment arm. Abnormal physical examination findings will also be listed.

8. PATIENT REPORTED OUTCOMES (PROs)

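### The SAP makes the Week 24 metabolic change endpoints descriptive, although the protocol assigns them the adjusted primary mixed model

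*SAP*

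**What the plan says.** Protocol 9.4.3.1 separates two groups of secondary metabolic endpoints. For those defined as change from baseline, "the same statistical model as described for the primary endpoint will be used for analysis"; all others are descriptive. The synopsis makes the same split: "For the metabolic endpoints of change from baseline, the same statistical model as described for the primary endpoint will be used for analysis". Protocol 9.4.2 defines that model as a linear mixed model with a random participant effect, adjusted for baseline BMI and the stratification factors, sex and race.

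SAP 6.2.2.1 has no such split. Its whole content is: "Secondary metabolic endpoints will be analyzed using descriptive statistics and frequency tabulations".

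The SAP still frames these endpoints as comparisons. SAP 6.2.1 says that "the secondary endpoints at Week 24 are defined for D/C/F/TAF FDC regimen (Immediate Switch Arm) versus INI + TAF/FTC ARV regimen" (the Delayed Switch Arm). A typical Week 24 objective in SAP 1.1.2.1 reads: "To assess changes in body composition when switching to D/C/F/TAF FDC (Immediate Switch Arm) compared to continuing the current INI + TAF/FTC ARV regimen".

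**The concern.** The two documents prescribe different analyses for the same endpoints. Protocol 9.4 gives the SAP the task of adding technical detail to the protocol's analyses, and the SAP amendment history records no change to this method and no reason for one.

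Two things are at stake:

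- **The contrast.** An analyst who follows the SAP produces summaries of each variable but no adjusted treatment difference and no interval for a difference. If the report later gives a between-arm result, its method will have been chosen after the fact or taken from a protocol section that the SAP contradicts. In an open-label trial that choice should be settled in writing beforehand.
- **Use of the data.** For endpoints measured at Weeks 4, 12 and 24, a participant with earlier values but none in the Week 24 window drops out of the Week 24 summary. The protocol's repeated-measures model would use those earlier values.

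**Working it through.** **Does any other SAP section restore the model?**

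| SAP section | Content | Restores it? |
|---|---|---|
| 5.1 | Mean, SD, 95% CI, median and range of each variable, with summaries by sex and race; most naturally read as per arm | No; no interval for a difference |
| 5.2.3, 5.2.4 | MMRM and its sensitivity analyses, for percent weight change only | No |
| 6.2.2.2 | Between-arm 95% CIs for categorical virologic outcomes | No |
| 7.2.2 | "Change from baseline to each scheduled time points will be summarized descriptively for chemistry, hematology, and urinalysis" | No |
| 7.3.2 | "Descriptive statistics for the actual values and changes from baseline (including BMI, weight) per timepoint will be presented" | No |
| Amendment history | No entry on this method | No |

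Where the SAP intends an arm comparison (5.2.3 and 6.2.2.2), it says so. Section 6.2.2.1 does not.

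**Which endpoints are affected?** Protocol 3.1 lists ten Week 24 metabolic change bullets on a continuous scale. The Schedule of Activities (Protocol 1.3) and the laboratory panels (Protocol 10.2) give the visits:

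- Weeks 4, 12 and 24: absolute weight, BMI, waist circumference, SBP/DBP (4).
- Weeks 4, 12 and 24 only if the chemistry and hematology panels are used: fasting glucose, HOMA-IR, HbA1c (3).
- One scheduled post-baseline value by Week 24: DEXA, fasting lipids, leptin/adiponectin (3).

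4 + 3 + 3 = 10. The second loss, unused earlier visits, applies to four to seven of them.

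**Design figure.** Protocol 9.2 gives n per arm = 16/ES². With ES = 0.54, 16/0.54² = 54.87, so 55. The exact t-test gives 54.81, with 80.1% power at 55. The plan's figure reproduces and is not touched by this point.

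**Half-width of an unadjusted between-arm 95% CI, in SD units** = t(0.975, 2n−2) × √(2/n):

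| n per arm | Basis | Half-width |
|---|---|---|
| 55 | planned | 0.378 |
| 75 | the 150 maximum after re-estimation | 0.323 |
| 50 | 10% of 55 missing, rounded (assumed) | 0.397 |
| 44 | 20% of 55 missing (assumed) | 0.424 |

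The half-width for one arm's mean at n = 55 is 0.270 SD. That interval does not estimate the difference.

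**Covariate adjustment** multiplies the half-width by √(1−R²). At n = 55:

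- R² = 0.02: 0.374 (1.0% narrower)
- R² = 0.05: 0.368 (2.5%)
- R² = 0.10: 0.359 (5.1%)
- R² = 0.25 (correlation 0.5, a generous assumption): 0.327 (13%)

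**Earlier visits.** If a fraction m lacks Week 24 but has an earlier value correlated ρ with it, likelihood-based variance divided by observed-case variance is 1 − mρ²:

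| m | ρ | Ratio | Half-width narrower by |
|---|---|---|---|
| 0.10 | 0.5 | 0.975 | 1.3% |
| 0.10 | 0.8 | 0.936 | 3.3% |
| 0.20 | 0.5 | 0.950 | 2.5% |
| 0.20 | 0.8 | 0.872 | 6.6% |

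The documents give no value for R², m or ρ.

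**The case against.** The conflict itself is not in dispute. The case for giving it less weight has five parts.

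- **The protocol does prespecify the model.** True, so the gap lies in the SAP and not in the two documents together. But both are in force and disagree, and the SAP is what the analyst will program from.
- **Some endpoints add little.** BMI uses the single screening height, so percent change in BMI equals percent change in weight, which keeps the full MMRM. Absolute weight is the same measurement on another scale. This stands as a comment on practical loss, although both endpoints are listed separately and lose the model the protocol gives them.
- **The missing-data effect may be smaller.** SAP 2.2 assigns early-discontinuation visits by day, so some discontinuers stay in the Week 24 window, and SAP 2.7 defines a last-available endpoint value. Neither provides a Week 24 value for someone with none in the window, and the SAP does not say the endpoint value is tabulated for metabolic variables. The only related figures are the drops from Week 24 to Week 48 in Protocol Table 3: 347 to 340 (2.0%) and 738 to 728 (1.4%), in other populations and over a later period. With m = 0.02 and ρ = 0.8 the gain is about 0.6%. The 1% to 7% range is therefore illustrative.
- **An unadjusted difference can be computed from each arm's N, mean and SD.** Yes, and randomization makes it unbiased apart from missing data. It would still not be the prespecified adjusted contrast.
- **The protocol model omits each outcome's own baseline value.** Adding it would be a sensible refinement. Its absence does not make restoring the protocol model unsound.

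**Conclusion.** The concern holds. The protocol assigns the adjusted primary model to the metabolic change endpoints; the SAP makes them descriptive without explanation. Ten Week 24 endpoint bullets, all framed as arm comparisons, lose their prespecified adjusted difference and between-arm interval. This conclusion rests on the text alone.

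The precision cost does rest on assumptions. It is 1% to 5% of the half-width from covariates at R² of 2% to 10%, plus 1% to 7% from earlier visits for the four to seven repeated endpoints. It would be near zero for the latter if very few Week 24 values are missing.

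The primary analysis, its alpha and its power are unaffected, and any intervals would be nominal. The point should be corrected, but it does not threaten the main result.

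**What to change.** In SAP 6.2.2.1, restore the protocol model for the Week 24 metabolic change endpoints. Report the treatment difference with a nominal 95% CI, adjusted for baseline BMI, sex and race:

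- **Repeated-measures model:** absolute weight, BMI, waist circumference, SBP and DBP.
- **Glucose, HOMA-IR and HbA1c:** the same model if the Weeks 4, 12 and 24 panel values are used, otherwise ANCOVA. SAP 6.2.1 lists HOMA-IR and HbA1c only at Weeks 24 and 48, so the SAP should state which values enter.
- **ANCOVA with the same covariates**, which is what the model reduces to with one post-baseline value: DEXA, lipids, leptin, adiponectin.
- **Descriptive, as in the protocol:** the proportions with more than 3% or 5% weight change and the medication-change proportions.
- **NAFLD and HAIR endpoints:** these are worded as change in a proportion, and the protocol rule is ambiguous for them. State that they stay descriptive.

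Adding each outcome's own baseline as a covariate is optional. If description alone is intended throughout, the SAP should say so and give the reason.

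The cost is a short SAP edit and reuse of the primary-model program. The data are already scheduled for collection, and no alpha or multiplicity claim is involved.
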